15.2.1 All Adverse Events

AEs will be summarized by worst severity (according to the National Cancer Institute – Common Terminology Criteria for Adverse Events (NCI-CTCAE) version 4.0) per subject, using MedDRA preferred term as event category and MedDRA primary system organ class (SOC) body term as Body System category.

If an AE is reported for a given subject more than once during treatment, the worst severity and the worst relationship to trial treatment will be tabulated. In case a subject had events with missing and non-missing grades, the maximum of the non-missing grades will be displayed.

The following overall frequency tables will be prepared by dose group and overall. In addition the tables will be provided by PT and primary SOC in alphabetical order:

- Any TEAE
- Any trial drug related TEAEs*
- Any serious TEAEs
- Any non-serious TEAEs
- Any trial treatment related serious TEAEs*
- Any TEAE by NCI-CTCAE severity grade (≥3, ≥4)
- Any trial drug related TEAE by NCI-CTCAE severity grade (≥3, ≥4)*
- Any TEAEs leading to death (TEAEs with Grade 5 or outcome "fatal" if grade 5 not applicable)
- Any trial drug related TEAEs leading to death (TEAEs with Grade 5 or outcome "fatal" if grade 5 not applicable)*

Tables annotated by * will be summarized as follows:

- Parts A and A2 with a summary for M4344
- Part B1: summaries for M4344, carboplatin, and M4344/carboplatin

The listing for all AEs (whether treatment-emergent or not) will include all the data fields as collected on the "Adverse Events" eCRF page.

Clinical trial.gov and EudraCT -requirements

Summary tables for non- serious adverse events excluding SAEs applying frequency threshold of 5% will be provided by study part. The non-serious AEs are not restricted to non-serious TEAEs.

15.2.2 Adverse Events Leading to Treatment Discontinuation

The following overall frequency tables based on AE actions will be prepared. In addition, summaries in terms of PT and primary SOC will be provided.

Temporary discontinuation

- Any TEAEs leading to temporary discontinuation of M4344 (Parts A, A2, and B1)
- Any TEAEs leading to temporary discontinuation of carboplatin (Part B1)
- Any TEAEs leading to temporary discontinuation of at least one trial drug (Part B1)
- Any TEAEs leading to temporary discontinuation of both trial drugs (Part B1)
- Any trial drug related TEAEs leading to temporary discontinuation of M4344 (Parts A, A2, B1)
- Any trial drug related TEAEs leading to temporary discontinuation of carboplatin (Part B1)

Permanent discontinuation

- Any TEAEs leading to permanent discontinuation of M4344 (Parts A, A2, and B1)
- Any TEAEs leading to permanent discontinuation of carboplatin (Part B1)
- Any TEAEs leading to permanent discontinuation of at least one trial drug (Part B1)
- Any TEAEs leading to permanent discontinuation of both trial drugs (Part B1)
- Any trial drug related TEAEs leading to permanent discontinuation of M4344 (Parts A, A2, B1)
- Any trial drug related TEAEs leading to permanent discontinuation of carboplatin (Part B1)

Dose reduction

- Any TEAEs leading to dose reduction of M4344 (Parts A, A2, and B1)
- Any TEAEs leading to dose reduction of carboplatin (Part B1)
- Any TEAEs leading to dose reduction of at least one trial drug (Part B1)
- Any TEAEs leading to dose reduction of both trial drugs (Part B1)
- Any trial drug related TEAEs leading to dose reduction of M4344 (Parts A, A2, B1)
- Any trial drug related TEAEs leading to dose reduction of carboplatin (Part B1)

15.3 Deaths, Other Serious Adverse Events, and Other Significant Adverse Events

15.3.1 Deaths

All deaths, deaths within 30 days after last dose of trial drug, and deaths within 60 days after first dose of trial drug will be tabulated based on information from the "End of Dosing" (Parts A and B1), "M4344 Administration Details" (Part A2), "Long-Term Follow-Up" (Parts A and B1), and "Death" (Part A2) eCRFs.

- Number of Deaths
- · Number of Deaths within 30 days after last dose
- Number of Deaths within 60 days after first dose

In addition, data relevant to subject deaths will be provided in an individual subject data listing together with selected dosing information (date of first / last administration of applicable trial drug). The death listing will also include the following:

- AEs with fatal outcome (list preferred terms of AEs with outcome=fatal),
- Flag for death within 30 days of last trial treatment (for each drug)
- Flag for death within 60 days of first trial treatment (for each drug)

15.3.2 Serious Adverse Events

Please refer to Section 15.2.1 for serious adverse event (SAE) related outputs. The listings of SAEs will also be provided with relevant information such as AE SOC/PT, start/stop date, toxicity grade, relationship to trial drug, action taken with study treatment, and outcome.

15.3.3 Other Significant Adverse Event

Safety summaries will be performed for special adverse event categories on "Blood bilirubin increased", "ALT/AST increased", and "Nausea/Vomiting". Special adverse event categories will be summarized by category and PT. The given terms constitutes of pooled MedDRA PTs.

Categories are defined as follows:

- Blood bilirubin increased: Bilirubin conjugated abnormal, Bilirubin conjugated increased, Bilirubin urine present, Bilirubinuria, Blood bilirubin abnormal, Blood bilirubin increased, Blood bilirubin unconjugated increased, CSF bilirubin positive, Hyperbilirubinaemia and Urine bilirubin increased
- ALT/AST increased: Standardised MedDRA Queries (SMQ) Narrow scope Drug related hepatic disorders – comprehensive search
- Nausea/Vomiting: Higher Level Term (HLT) of Nausea and vomiting symptoms

15.4 Clinical Laboratory Evaluation

Analysis set: SAF

All statistical analyses of laboratory values will be performed using SI units.

Laboratory results will be classified according to the latest version of NCI-CTC as provided by the central or local laboratory. Additional laboratory results that are not part of NCI-CTC will be presented according to the categories: below normal limits, within normal limits and above normal limits (according to the laboratory normal ranges). For a complete list of laboratory tests to be analyzed, please refer to Appendix I.

The worst on-treatment grade will be summarized considering only subjects with on-treatment laboratory samples: Laboratory tests by NCI-CTC grade (0, 1, 2, 3, 4, any).

Quantitative data will be examined for trends using descriptive statistics (mean, StdDev, median, Q1, Q3, minimum, and maximum) of actual values and changes from baseline to each visit over time. The changes computed will be the differences from baseline. Qualitative data based on reference ranges will be described according to the categories (i.e. Low, Normal, and High). The number of subjects with clinical laboratory values below, within, or above normal ranges at baseline compared to endpoint will be tabulated for each test by treatment. Shift tables of baseline versus endpoint (as well as the worst value at any on-treatment visit) will be presented. Abnormalities classified according to NCI-CTCAE toxicity grading will be described using the worst grade.

NCI-CTC grades available:

- Number and percentage of subjects with any, NCI-CTC grade 0, 1, 2, 3, 4, 3 or 4 laboratory abnormalities under treatment – (worst case)
- Shifts in toxicity grading from baseline NCI-CTC grade to worst on-treatment NCI-CTC grade
 The highest NCI-CTC grade during the on-treatment period is considered as the worst grade for the summary.

NCI-CTC grades not available:

Number of subjects with shifts from baseline normality to post-baseline normality based on worst on-treatment value

The normality categories will be produced based on the normal range for all hematology and blood chemistry parameters as follows:

- Baseline: Low/Normal/High/Missing/Overall
- Worst on-treatment: Low/Normal/High/Missing/Overall

Normal category includes low values for high parameters and high values for low parameters.

Subjects without post baseline laboratory samples will be excluded from analyses with respect to values after the baseline.

The following figures and tables will be provided for each test mentioned above:

- Boxplots of laboratory values at baseline and by on-treatment time point
- Boxplots of the absolute change from baseline by on-treatment time point
- A plot of peak on-treatment alanine aminotransferase (ALT) versus peak on-treatment total bilirubin, both relative to the upper limit of normal (ULN) will be provided. This eDISH plot (evaluation of drug-induced serious hepatotoxitiy) will have reference lines at 3×ULN for ALT and at 2×ULN for total bilirubin.

Boxplots for laboratory parameters where toxicity grades are defined based on the ratio of the parameter values and the ULN will not be displayed using the unit of measurement but instead using the ratio of the measured value over ULN. This comprises alkaline phosphatase (ALP), ALT, aspartate aminotransferase (AST), bilirubin, creatinine, and lactate dehydrogenase (LDH).

Coagulation parameters

Coagulation parameters are only assessed at the screening visit, so these will be listed.

Urinalysis

All urinalysis and microscopic analysis will be presented in listings only.

For all tests not mentioned above but present in the clinical data, a listing with the number of subjects with at least one result for the respective test will be provided. This listing will include data from scheduled and unscheduled time points.

Individual subject laboratory values that are outside the normal range will be included in a separate data listing along with corresponding normal ranges. Any out-of-range values that are identified by the investigator as being clinically significant will be flagged.

- Listing of laboratory values by category (hematology, serum chemistry, urinalysis, and coagulation)
- Listing of abnormal laboratory values

In addition, a listing displaying parameters with at least one value with grade ≥ 3 will be provided. For each subject, only parameters where at least one value has grade ≥ 3 will be displayed (all visits for the corresponding parameter will be displayed in the listing).

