15.3 Primary Endpoint: Clinical Laboratory Evaluation

Parameters with NCI-CTCAE grades available:

Laboratory results will be classified according to the NCI-CTCAE criteria version 5.0. Some of the toxicity gradings are based on laboratory measurements in conjunction with clinical findings. Non-numerical qualifiers (with the exception of fasting flags) will not be taken into consideration in the derivation of CTCAE criteria. For example, hypokalemia Grade 1 and Grade 2 are only distinguished by a non-numerical qualifier (symptomatic and intervention indicated) and therefore Grade 2 will not be derived. Abnormalities classified according to NCI-CTCAE toxicity grading version will be described using the worst on-treatment grade. For those parameters which are graded with two directions of toxicities such as potassium (hypokalemia/hyperkalemia), the toxicities will be summarized separately. Low direction toxicity (e.g., hypokalemia) grades will be set to 0 when the variables are derived for summarizing high direction toxicity (e.g., hyperkalemia), and vice versa.

The laboratory toxicities will be tabulated with counts of participants and percentages during the on-treatment period. The denominator to calculate percentages for each laboratory parameter is the number of participants in the analysis population. Subjects without an on-treatment result or results which are not CTCAE gradable will be counted in the "Missing" category.

- The summary of laboratory parameters by CTCAE grade table will include number and percentage of participants with Grade 1, 2, 3, 4, 3/4, and any grade (1 to 4), laboratory abnormalities during the on-treatment period.
- The shift table will summarize baseline CTCAE grade versus the worst on-treatment CTCAE grade. The highest CTCAE grade during the on-treatment period is considered as the worst grade for the summary.

The following parameters are CTCAE-gradable:

Hematology:

Hemoglobin, leukocytes, lymphocytes, neutrophils/absolute neutrophil count, platelet count.

Serum Chemistry:

Albumin, alkaline phosphatase, alanine aminotransferase (ALT), amylase, aspartate aminotransferase (AST), total bilirubin, cholesterol, creatinine, creatine kinase, potassium, sodium, magnesium, calcium, glucose, gamma glutamyl transferase (GGT), lipase, phosphates, triglycerides.

Please see the further details of NCI-CTCAE gradable parameters in the Appendix.

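### Parts A/A2/B1 plan: the ALT/AST category is defined by a hepatic-disorders query, and laboratory grades follow an undated CTC version while AEs use v4.0

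*SAP*

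**What the plan says.** The SAP file holds two plans: one for Parts A, A2 and B1 (version dated 24 August 2018) and one for Part C (14 April 2021). The point concerns the first.

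**AE category.** Section 15.3.3 sets up three special AE categories. Blood bilirubin is an explicit list of ten preferred terms, all naming bilirubin. Nausea/vomiting is one MedDRA higher level term with a matching name. The third is defined as "ALT/AST increased: Standardised MedDRA Queries (SMQ) Narrow scope Drug related hepatic disorders – comprehensive search". On reporting, the section says "Special adverse event categories will be summarized by category and PT".

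**Grading version.** Section 15.2.1 grades AE severity by "Common Terminology Criteria for Adverse Events (NCI-CTCAE) version 4.0) per subject" and plans, among others, a table described as "Any TEAE by NCI-CTCAE severity grade (≥3, ≥4)". For laboratory values Section 15.4 says "Laboratory results will be classified according to the latest version of NCI-CTC as provided by the central or local laboratory". A later sentence in that section names the criteria with no version at all: "Abnormalities classified according to NCI-CTCAE toxicity grading will be described using the worst grade".

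The Part C plan, Section 15.3, is specific: "Laboratory results will be classified according to the NCI-CTCAE criteria version 5.0". Its Section 15.1 uses version 5.0 for AEs as well.

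**The concern.** AEs and clinical laboratory values are both named under the primary safety endpoint for Parts A, A2 and B1 (Section 5), and Section 4 intends the results for the study report, regulatory submissions and manuscripts. Readers will take the tables at face value.

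A row labelled as raised ALT/AST will be read as the number of subjects with a reported transaminase rise. It is likely to be set beside the plot of peak ALT against peak bilirubin in Section 15.4, which does measure ALT. If the row is filled by a query on hepatic disorders, the comparison is not like with like.

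Similarly, laboratory abnormalities of grade 3 or 4 will be compared with TEAEs of grade 3 or higher. If the two sets of grades rest on different versions of the criteria, part of any difference could come from the version. A grading rule tied to whatever version is latest also cannot be reproduced from the plan alone.

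**Working it through.** The plan gives no figure to reproduce and no arithmetic applies. The check is a comparison of the texts.

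**1. Category label against category content (Section 15.3.3)**

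| Category label | Defined by | Does the definition match the label by name? |
|---|---|---|
| Blood bilirubin increased | Ten listed bilirubin preferred terms | Yes |
| Nausea/Vomiting | Higher level term for nausea and vomiting symptoms | Yes |
| ALT/AST increased | Narrow-scope SMQ, comprehensive search for drug-related hepatic disorders | No: the query names hepatic disorders, the label names two enzymes |

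The terms in the SMQ are not in the documents, so the judgement rests on its name and stated scope. Narrow scope restricts the query, but nothing in the text restricts it to transaminases. The table has a category row and preferred-term rows. The term rows carry their own names and are unaffected; the category row is the one with the wrong label.

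**2. Grading version**

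| Output | Parts A/A2/B1 plan | Part C plan |
|---|---|---|
| AE severity | Version 4.0 (Section 15.2.1) | Version 5.0 (Section 15.1) |
| Laboratory grades | Latest version, no number or date (Section 15.4) | Version 5.0 (Section 15.3) |

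The Part C plan shows that a version later than 4.0 exists, so latest and 4.0 need not be the same. It also shows the sponsor using one named version for both kinds of data.

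The Section 15.4 sentence can be read in two ways:

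- *The laboratory provides the results.* One latest version is then applied to all subjects. The version is still unnamed and may still differ from the AE version.
- *The laboratory provides the grading or its version.* The version can then also differ between laboratories.

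The AE and laboratory versions can differ under either reading. Timing adds to this: Section 6.1 locks the database for each study part and keeps Part A2 in a separate database, and Section 15.4 does not say at which date latest is judged.

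**3. One internal sign that gradability is not settled.** Section 15.4 of the Parts A/A2/B1 plan includes LDH among the parameters whose toxicity grades are defined by the ratio to the upper limit of normal. Section 15.3 of the Part C plan places LDH among parameters without grades under version 5.0. The documents do not show whether this reflects the version or a slip in one plan.

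**4. Outputs affected.** For step 1, the category row in the Section 15.3.3 summary. For step 2, the Section 15.4 tables by grade (including grade 3 or 4), the shifts from baseline to worst grade, and the listing of parameters with a value of grade 3 or higher. Section 15.1 takes DLT information from the DLT field on the AE page of the eCRF, so the MTD uses neither the laboratory grades nor the SMQ category.

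**The case against.** The best case on the other side is that these are matters of wording in descriptive outputs.

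- The two items are unrelated. The special category groups AE terms and has no stated grade, so no CTC version enters it. A reader might infer that one toxicity is counted under conflicting definitions, but no planned table does that. This stands, and the defects are kept apart here.
- A reader might infer that the ALT/AST count will be too high, or will double-count bilirubin events. The content of the SMQ is not in the documents, its narrow scope limits it, and the section does not say that the categories are exclusive or added together. A subject appearing in two categories would not in itself be an error. This stands; only the mismatch between label and definition is shown.
- A reader might infer that laboratories will in fact use different versions, so that dose groups cannot be compared. The sentence is ambiguous. The plan also uses latest-version wording for MedDRA and WHO-DD, where it points to one current release. This stands as far as mixing within a table goes, which is possible but not established. It does not answer the difference from the AE version.
- Part C has its own plan, so it does not show that data from Parts A, A2 and B1 mix versions. Correct; it shows only that a later version exists.
- AE tables come from reported events and laboratory tables from measured values, so they can differ under a shared version. Correct. Aligning the versions removes one source of difference, not all of them.
- The ALT against bilirubin plot, the boxplots in multiples of the upper limit of normal and the listings with normal ranges do not depend on the CTC grade. Correct, and this limits the harm to hepatic interpretation.

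**Conclusion.** Both defects hold as stated rules that would be followed as written, not as missing detail.

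The first can be read off the page: a category labelled for ALT and AST is defined by a query named for hepatic disorders, so its category-level count cannot be read as transaminase rises. This assumes only that the query covers what its name says.

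The second is a grading version left open for laboratory values beside a fixed version 4.0 for AEs. The laboratory grade outputs may rest on a different version from the AE grade outputs and, on one reading of the sentence, on more than one version.

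The size of either effect cannot be derived: the documents contain neither version's grading table, no SMQ term list and no data. The consequences are limited to descriptive summaries of the primary safety endpoint. A reader might infer that dose selection is at risk, but the MTD rests on the DLT flag in the eCRF and is unaffected.

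**What to change.** **Section 15.3.3.** Define the ALT/AST category by a list of preferred terms for ALT, AST and transaminases increased or abnormal, in the same form as the bilirubin list. Keep the SMQ as a separate category under a hepatic disorders label. At the least, rename the present category to match its query.

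**Section 15.4.** Name CTCAE version 4.0, as for AEs, in place of the latest version. State that all laboratory grades for Parts A, A2 and B1 are derived centrally from numeric values and normal ranges, and not taken from laboratory-supplied grades. Section 15.3 of the Part C plan already has a rule for criteria with non-numerical qualifiers and for parameters graded in two directions; the same approach can be written in here with the version changed. Check the list of parameters graded by ratio to the upper limit of normal, LDH in particular, against the named version.

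The cost is a few lines of SAP text, one derivation program for laboratory grades and one additional AE category. No new data collection is needed.

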15.5 Vital Signs

Analysis set: SAF

Vital sign values and their changes from baseline will be summarized for each scheduled visit on treatment.

The changes of vital sign measurements from baseline to most extreme post-baseline on-treatment change after start of first dose of trial drug will be presented. The categorization of maximum changes is grouped as follows:

Vital Sign Baseline Category	Change from Baseline Category
Body temperature increase	<1°C, 1-<2°C, 2-<3°C, ≥ 3 °C
Heart rate increase from baseline <100 bpm; ≥ 100 bpm	≤20 bpm, >20 – 40 bpm, >40 bpm
Heart rate decrease from baseline <100 bpm; ≥ 100 bpm	≤20 bpm, >20 – 40 bpm, >40 bpm
SBP increase from baseline <140 mmHg; ≥ 140 mmHg	≤20 mmHg, >20 – 40 mmHg, >40 mmHg
SBP decrease from baseline <140 mmHg; ≥ 140 mmHg,	≤20 mmHg, >20 – 40 mmHg, >40 mmHg
DBP increase from baseline <90 mmHg; ≥ 90 mmHg	≤20 mmHg, >20 – 40 mmHg, >40 mmHg
DBP decrease from baseline <90 mmHg; ≥ 90 mmHg,	≤20 mmHg, >20 – 40 mmHg, >40 mmHg
Respiration rate increase from baseline $<$ 20 bpm; \ge 20 bpm	≤5 bpm, >5 – 10 bpm, >10 bpm
Respiration rate decrease from baseline $<$ 20 bpm; \geq 20 bpm	≤5 bpm, >5 – 10 bpm, >10 bpm

The following summaries will be prepared for vital sign parameters as grouped above considering only subjects with on-treatment values:

- Maximal Shifts (changes in categories)
- Listing of highest change per subject

An additional subject data listing will present all changes from baseline reported in the highest categories.

15.6 Other Safety or Tolerability Evaluations

Analysis set: SAF

ECG

Descriptive statistics of observed values and changes from baseline at each scheduled visit will be provided for ECG measures of PR interval, QRS interval, QT interval, QTc interval (derived using Fridericia's correction method), and HR.

The Fridericia's Correction (QTcF) is derived as follows:

Fridericia's Correction (QTcF)
$$QTc_f = \frac{QT}{\sqrt[3]{RR}}$$

where: RR = RR-interval measured in seconds.

Shifts from normal baseline values to abnormal on-treatment results will be summarized. Listings of 12-lead ECG data will also be provided with all relevant information such as visit, date/time of assessment, measurement, and results.

- Shifts from baseline to worst on-treatment value
- Listing of ECG results

16 Analyses of Other Endpoints

